5.0 STUDY CALENDAR

Pre-Study Testing Intervals for all patients

- To be completed ≤ 14 DAYS before Pre-registration: All laboratory studies, history and physical.
- To be completed ≤ 28 DAYS before registration: Any imaging utilized for tumor measurement per protocol.

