3.1 On-study Guidelines

This clinical trial can fulfill its objectives only if patients appropriate for this trial are enrolled. All relevant medical and other considerations should be taken into account when deciding whether this protocol is appropriate for a particular patient. Physicians should consider the risks and benefits of any therapy, and therefore only enroll patients for whom this treatment is appropriate.

Physicians should consider whether any of the following may render the patient inappropriate for this protocol:

- Psychiatric illness which would prevent the patient from giving informed consent.
- Medical condition such as uncontrolled infection (including HIV), uncontrolled diabetes mellitus or cardiac disease which, in the opinion of the treating physician, would make this protocol unreasonably hazardous for the patient.
- Patients with a “currently active” second malignancy other than non-melanoma skin cancers. Patients are not considered to have a “currently active” malignancy if they have completed therapy and are free of disease for ≥ 3 years.

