3.2 Pre-registration Eligibility Criteria

3.2.1 Women who agree to undergo a standard of care core biopsy of recurrent or metastatic breast cancer (see Section 6.2.2 for details of biopsy) to confirm the ER+ ($\geq 10\%$ nuclear staining) and HER2 negative status (see Sections [3.3.5](#) and [3.3.6](#)).

3.2.2 Patient must have been previously treated with an aromatase inhibitor (either letrozole, anastrozole or exemestane) either in the adjuvant or metastatic setting, and have one of the following types of primary or secondary endocrine resistant disease.

Primary Clinical Resistance is defined as one of the following:

- Recurrence within the first 2 years of adjuvant endocrine therapy while on aromatase inhibitor therapy
- Progression within first 6 months of initiating first-line endocrine therapy (either aromatase inhibitor or fulvestrant containing regimen) for the treatment of metastatic breast cancer.

Secondary Clinical Resistance is defined as one of the following:

- Recurrence after year 2 while receiving adjuvant aromatase inhibitor therapy, or within 12 months of completing adjuvant aromatase inhibitor therapy.
- Progression occurring 6 or more months after initiating the first endocrine therapy for metastatic disease (either fulvestrant or aromatase inhibitor containing regimen).

3.2.3 Patients with a history of measurable disease as defined by RECIST criteria (See Section [11.0](#)) or bone only disease are eligible. Note: Those patients with non-measurable disease and bone metastases are eligible.

3.2.4 No history of tumors involving spinal cord or heart.

___ 3.2.5 No current evidence of visceral crisis or lymphangitic spread.

___ 3.2.6 No known brain metastases.

___ 3.2.7 Women age \geq 18 years.

___ 3.2.8 **Women must be postmenopausal**

Postmenopausal status is verified by:

- Prior bilateral surgical oophorectomy, or
- Age \geq 60 years, or
- Age $<$ 60 with no menses for $>$ 1 year with FSH and estradiol levels within postmenopausal range, according to institutional standard.

___ 3.2.9 **Prior treatment**

- No more than two prior chemotherapy regimens in the metastatic setting.
- Prior treatment with an aromatase inhibitor (either anastrozole, letrozole or exemestane), either in the adjuvant or metastatic setting is required.
- Unlimited prior endocrine regimens in the metastatic setting, which may have included everolimus or a CDK4/6 inhibitor (such as a palbociclib, abemaciclib or ribociclib) containing regimens.

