- Prior tamoxifen treatment is allowed in the adjuvant setting, but patients must not have experienced relapse within 1 year of stopping tamoxifen.
- No prior treatment with tamoxifen in the metastatic setting.
- No prior treatment with endoxifen.
- Patients who have not fully recovered from acute, reversible effects of prior therapy regardless of interval since last treatment are not eligible to participate in this study. **EXCEPTION:** Neuropathies – if grade 2 neuropathies have been stable for at least 3 months since completion of prior treatment patient is eligible.

___ 3.2.10 Not receiving any medications or substances that are strong inhibitors of CYP2D6 (see [Appendix II](#)).

___ 3.2.11 Not receiving any other investigational agents.

___ 3.2.12 **No uncontrolled intercurrent illness including, but not limited to:**

- Ongoing or active infection
- Symptomatic congestive heart failure
- Unstable angina pectoris
- Uncontrolled symptomatic cardiac arrhythmia
- Uncontrolled hypertension (defined as blood pressure $>$ 160/90)

3.2.13 None of the following co-morbid conditions:

- Cataracts of grade 2 or greater as per CTCAE Version 4.0
- Retinopathy of grade 2 or greater as per CTCAE Version 4.0

Note: Patients that have cataracts that do not require surgery are eligible.

Note: Serious adverse events will be reported on CTEP-AERS using CTCAE v5.0.

- DVT/PE within the past 6 months

Note: Patients that are on anticoagulant therapy for maintenance are eligible as long as the DVT and /or PE occurred > 6 months prior to enrollment, and there is no evidence for active thrombosis (either DVT or PE).

3.2.14 No other active second malignancy other than non-melanoma skin cancers within 3 years of pre-registration. A second malignancy is not considered active if all treatment for that malignancy is completed and the patient has been disease-free for at least 3 years prior to pre-registration.

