3.2.15 ECOG Performance Status: 0-2

3.2.16 Able to swallow oral formulation of the study agent.

3.2.17 Required Initial Laboratory Values:

Hemoglobin	≥	9 g/dL
Platelet Count	≥	75,000/mm ³
Creatinine	≤	1.5 x upper limits of normal ULN
Total Bilirubin	≤	1.5 x upper limits of normal (ULN)
AST	≤	2.5 x upper limits of normal (ULN)
		For patients with liver metastasis: ≤ 5 x upper limits of normal (ULN)

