3.3 Registration Eligibility Criteria

Registration must be completed within 28 days of Pre-registration

3.3.1 Patients with either measurable disease as defined by RECIST criteria (See Section 11.0) or bone only disease are eligible. Note: Those patients with both non-measurable disease and bone metastases are eligible.

- Non-measurable bone only disease: Non-measurable bone only disease may include any of the following: blastic bone lesions, lytic bone lesions without a measurable soft-tissue component, or mixed lytic-blastic bone lesions without a measurable soft-tissue component.
- Lytic bone lesions, with an identifiable soft tissue component, evaluated by CT or MRI, can be considered as measurable lesions if the soft tissue component otherwise meets the definition of measurability previously described.

3.3.2 No tumors involving spinal cord or heart.

3.3.3 No visceral crisis, lymphangitic spread or known brain metastases: Visceral crisis is not the mere presence of visceral metastases, but implies severe organ dysfunction as assessed by symptoms and signs, laboratory studies, and rapid progression of disease.

3.3.4 Histologic confirmation, from the A011203 Pre-registration biopsy, by institutional/local pathologist of either locally advanced or metastatic breast cancer that is estrogen receptor positive and HER2 negative.

Those patients with bone only disease with either no tumor or insufficient tumor for ER/PR and HER2 staining after the bone biopsy are still eligible to participate in this study.

3.3.5 Estrogen receptor positive disease is defined as > 10% nuclear staining.

3.3.6 **HER2 Negative Disease as per 2013 ASCO/CAP guidelines, one of the following must apply:**

- 1) 0 or 1+ by IHC and not amplified by ISH
- 2) 0 or 1+ by IHC and ISH not done
- 3) 2+ by IHC and not amplified by ISH or
- 4) IHC not done and not amplified by ISH

3.3.7 **None of the following therapies are allowed prior to registration*:**

- Chemotherapy \leq 2 weeks
- Immunotherapy \leq 2 weeks
- Biologic therapy \leq 2 weeks
- Hormonal therapy \leq 2 weeks
- Monoclonal antibodies \leq 2 weeks
- Radiation therapy \leq 2 weeks
- Anti-Her-2 or other “targeted” (e.g. mTOR) therapy \leq 2 weeks

*Note: Any toxicities derived from these therapies must be \leq grade 2 prior to starting study therapy.

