4.4 Pre-registration Requirements

- Patient pre-registration can occur only after screening evaluation is complete, pre-registration eligibility criteria have been met, and the study site is listed as "approved" in the CTSU RSS.
- **Informed consent:** the patient must be aware of the neoplastic nature of his/her disease and willingly consent after being informed of the procedure to be followed, the experimental nature of the therapy, alternatives, potential benefits, side-effects, risks, and discomforts. Current human protection committee approval of this protocol and a consent form is required prior to patient consent and pre-registration.

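### The laboratory entry limits apply only at pre-registration, so qualifying results can be 42 days old at randomization and the repeat draw has no acceptance limit

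*Combined protocol and SAP*

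**What the plan says.** Eligibility is assessed in two steps. The numeric laboratory limits belong to the first. Section 3.2.17, headed "Required Initial Laboratory Values", sits within the pre-registration criteria and covers hemoglobin, platelets, creatinine, total bilirubin and AST. Section 4.4 fixes when they are tested: "Patient pre-registration can occur only after screening evaluation is complete, pre-registration eligibility criteria have been met". Section 5.0 gives the allowed age of the tests at that step: "To be completed ≤ 14 DAYS before Pre-registration: All laboratory studies, history and physical".

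The second step is registration, at which the patient is randomized. Section 3.3 opens with "Registration must be completed within 28 days of Pre-registration". Its criteria (3.3.1 to 3.3.7) contain none of the 3.2.17 limits. Section 4.6 makes treatment assignment follow from the local pathology result and mentions no laboratory check.

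The calendars in Sections 5.1 and 5.2 mark AST, creatinine, bilirubin and the blood count twice: once before pre-registration, and again in the pre-registration period, days -28 to -1. No acceptance limit is attached to the second draw.

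The schema lists the limits without tying them to either step.

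**The concern.** Entry limits on blood counts and on liver and kidney function are meant to keep out patients for whom the study drug may be unsafe. They do that best when they describe the patient close to randomization. Here they are checked once, possibly six weeks earlier, in women with endocrine-resistant advanced disease whose values may change in the meantime. The protocol collects a newer result on the same five analytes but does not make randomization depend on it. A patient can therefore be randomized with a current value that the protocol's own limit would have rejected at pre-registration.

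Only patient safety is at stake. The limits and the gap are the same for both arms and act before allocation, so no bias or effect on power is alleged.

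**Working it through.** The documents state no total age for the qualifying results, so there is no figure of theirs to reproduce. The check adds the stated windows.

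**Inputs**
- Qualifying tests to pre-registration: at most 14 days (Section 5.0).
- Pre-registration to registration/randomization: at most 28 days (Section 3.3).
- Repeat draw: days -28 to -1 before registration (Sections 4.5, 5.1, 5.2).
- Registration to first dose: at most 14 days (Section 7.0).
- Chemotherapy and the other listed therapies: barred in the 2 weeks before registration (Section 3.3.7).

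**Age of the qualifying results**
- At randomization, now: 14 + 28 = 42 days.
- At first dose, now: 42 + 14 = 56 days. A newer result must exist by then, because results from before registration may serve for cycle 1 day 1 only if taken no more than 21 days before treatment.
- At randomization, if the limits also governed the repeat draw: 28 days. The gain is 42 - 28 = 14 days.

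In the 42-day case the qualifying tests fall outside days -28 to -1, so they cannot double as the calendar's second draw. A newer result is required in exactly the case where the first is oldest.

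**Room for chemotherapy between the two steps.** Recovery from earlier treatment is checked at pre-registration: patients "not fully recovered from acute, reversible effects of prior therapy regardless of interval since last treatment are not eligible to participate" (Section 3.2.9). With pre-registration on day -28 and the last 14 days barred, chemotherapy could be given on days -28 to -15, so 28 - 14 = about 14 days. The fix does not shorten this worst case, because the repeat draw may itself be on day -28. Nothing in the documents suggests that such treatment is common.

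**Whether another rule closes the gap**
- Section 3.1 tells physicians to "only enroll patients for whom this treatment is appropriate". This is judgment, with no limit attached.
- Section 3.2.9 is stricter than a grade 2 cap, but it is checked at pre-registration.
- Section 3.3.3 excludes visceral crisis and refers to laboratory studies, but requires severe organ dysfunction and gives no values.
- The note to Section 3.3.7 caps toxicity at grade 2 before study therapy, but only toxicity from the listed prior treatments. Decline from the disease itself is not covered, and the cap is not the 3.2.17 limits.
- The 21-day rule for cycle 1 day 1 governs the age of the results and sets no value for starting treatment.
- Sections 8.2.1 and 8.2.2 act on treatment and on grade 3 or 4 events. For Z-Endoxifen they name lymphopenia, thrombocytopenia and hypertriglyceridemia, plus non-hematologic events attributed to the drug. Anemia is not named. A creatinine, bilirubin or AST abnormality present before the first dose could not be attributed to the drug.

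Each rule covers part of the gap. None applies the five entry limits at randomization.

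**Whether restating a criterion at registration would be out of keeping.** Section 3.2.4 reads "No history of tumors involving spinal cord or heart", and Section 3.3.2 reads "No tumors involving spinal cord or heart". Sections 3.3.1 to 3.3.3 likewise repeat disease type, visceral crisis, lymphangitic spread and brain metastases from Sections 3.2.3 to 3.2.6. The protocol already re-checks some pre-registration items at the second step.

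**The case against.** The strongest reply is that this is a deliberate two-step design. General fitness is checked before the biopsy and disease status at registration. Section 5.0 follows the same pattern, timing imaging to registration and laboratory tests, history and physical to pre-registration. Section 3.3 also leaves out menopausal status, CYP2D6 inhibitors, intercurrent illness, thrombosis, performance status and other items, so laboratory values are not singled out. This reading is plausible, and it is why the point is a design choice and not an inconsistency. It does not explain why the same five analytes are redrawn with no rule for acting on the result.

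A second reply is that safety turns on the first dose, and the 21-day rule guarantees a newer result by then. That is correct, but no starting value is attached to that result, and by then the patient has been randomized.

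Third, the grade 2 cap in the 3.3.7 note covers the chemotherapy scenario and runs up to the start of treatment, later than the proposed fix would. This stands for treatment-related abnormalities and leaves deterioration from other causes.

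Fourth, Section 12.7 requires stopping therapy if the protocol's constraints harm the patient. It acts after entry, so it mitigates the problem without preventing it.

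Finally, the benefit is modest. The 42-day figure needs both windows at their maximum, a suitable earlier biopsy can shorten the wait, and the fix still permits a 28-day-old result. Since the schema does not assign the limits to a step, some sites may already apply them at registration. All of this stands and limits the severity.

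**Conclusion.** The concern holds, as a minor patient-safety point. The 3.2.17 limits bind only at pre-registration, the qualifying results can be up to 42 days old at randomization, and the scheduled repeat draw carries no acceptance limit.

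The 42 days assume that both windows are used in full and that sites follow Sections 3.2, 3.3 and 4.4 as written. The documents give no rate of laboratory deterioration between the two steps, so the number of patients affected is unknown. Confidence is high in the reading and the arithmetic. It does not extend to how often the gap would matter.

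**What to change.** Add one criterion to Section 3.3: the limits in 3.2.17 must be met on the most recent laboratory results before registration/randomization, using the pre-registration-period draw already in the calendars of Sections 5.1 and 5.2.

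This needs one line of protocol wording and no new test, visit or threshold, and it gives every site the same explicit rule. The maximum age of the qualifying results falls from 42 to 28 days. The lag is shortened, not removed. The cost is possibly a few more screen failures before randomization.

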5.1 Study Arm 1 Z-Endoxifen HCl

	Prior to pre-registration	Pre-registration Period (any time during days -28 to -1)	Days 1 of each treatment cycle*	At PD or discontinuation of protocol therapy**
Tests & Observations				
History and physical, weight, PS	X		X	X
Height	X			
Pulse, Blood Pressure	X		X	X
Adverse Event Assessment			X	X
Patient Medication Log			X(1)	X(1)
Registration Fatigue/Uniscale Assessment		A		
Standard of care biopsy of either locally recurrent or metastatic breast cancer is required for determination of ER, PR and HER2		B		
Laboratory Studies				
AST, creatinine, Total Bilirubin	X	X	X	X
Complete Blood Count, Differential, Platelets	X	X	X	X
Albumin, Alk Phos, ALT, calcium, glucose, phosphorous, sodium, potassium,		X	X	X
Fasting lipid profile (total Cholesterol, LDL, HDL, triglycerides)		C	C	
Imaging Tumor Measurements/Evaluation of Indicator Lesions				
CT/MRI		D, E, F	D,	D, E
Bone Scan/PET-CT scan		D, E, F	E	E
Correlative Studies: For Patients who consent to participate				
Tissue and Blood samples	See Sections 6.0 and 14.0 .			

* Cycle length is 21 days. Labs completed prior to registration may be used for day 1 of cycle one tests if obtained ≤ 21 days prior to treatment. For subsequent cycles, labs, scans, tests and observations may be obtained no more than +/- 3 days prior to day 1 of treatment.

** After treatment discontinuation, patients will be followed yearly for a maximum of 5 years from study registration/randomization (see Section [12.3](#)).

1. Medication Log must begin on the day the patient begins study medication and must be completed per protocol until treatment discontinuation (see Section [7.4](#)).

- A. To be completed after Pre-registration and prior to treatment, and will take approximately a minute to complete (see Section [1.8](#) and [Appendix I](#)).
- B. A standard of care biopsy of locally recurrent or metastatic breast cancer during the pre-registration period is required to confirm ER, PR and HER2 status by an institutional/local pathologist and for submission of a research block for optional correlative studies. **However**, if a prior biopsy was performed on a locally recurrent/metastatic site within 90 days of pre-registration, and no anti-cancer therapy was administered during that time period, that specimen can be used for confirmation of ER/PR/HER2 and for submission of tissue for optional correlative studies.
- C. Lipid profile is required at Pre-registration (baseline), cycles 2, 4 and 8 and thereafter at the discretion of the treating physician.
- D. Acceptable imaging modalities for measurable disease include: a CT, spiral CT, MRI, and chest x-ray. A FDG-PET scanning is allowed to complement CT scanning in assessment of progressive disease.
- E. Tumor measurements are required during the pre-registration period (days -28 to -1), at completion of cycles 2, 4, and 6 (approximately, every 6 weeks) then every 4 cycles (approximately every 3 months) thereafter until disease progression, as determined in Section [11.0](#). The same imaging method utilized at baseline must be used at all disease assessments and must include all target and non-target lesions recorded at baseline.

For patients without bone metastases, bone scans after the baseline bone scan are at the discretion of the treating physician. See Section [11.0](#) for acceptable modalities for tumor imaging.

For patients with non-measurable bone only disease, follow-up imaging either with PET/CT or bone scan should be performed at the time of tumor assessment. The same imaging method utilized at baseline must be used at all tumor assessments.

- F. Need not be repeated if performed before pre-registration period, but not more than 28 days prior to registration.

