- G. Baseline imaging tumor measurements and laboratory studies for patients crossing over to the Z-Endoxifen HCl phase, are those taken at the time of disease progression on the Tamoxifen treatment arm. Z-Endoxifen HCl treatment should start no more than 28 days after documentation of disease progression.

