8.2.2 Z-Endoxifen HCl

If a grade 3 or 4 lymphopenia, thrombocytopenia, or hypertriglyceridemia, hold Z-Endoxifen HCl therapy until toxicity resolves to < grade 2. Reduce dose to 40mg daily. If the toxicities do not resolve to ≤ grade 1 or baseline severity within 21 days (1 cycle), treatment is to be discontinued and the patient will go to event monitoring. If toxicity recurs, treatment is to be discontinued.

If a grade 3 or 4 non-hematologic event that is attributed to Z-Endoxifen HCl occurs, hold therapy until toxicity resolves to ≤ grade 1 or back to baseline (if baseline is grade 2) and reduce dose to 40mg daily. If the toxicities do not resolve to ≤ grade 1 or baseline severity within 21 days (1 cycle), treatment is to be discontinued and the patient will go to event monitoring.

The prompt reporting of adverse events is the responsibility of each investigator engaged in clinical research, as required by Federal Regulations. Adverse events must be described and graded using the terminology and grading categories defined in the NCI’s Common Terminology Criteria for Adverse Events (CTCAE), Version 4.0. The CTCAE is available at:

http://ctep.cancer.gov/protocolDevelopment/electronic_applications/ctc.htm. Attribution to protocol treatment for each adverse event must be determined by the investigator and reported on the required forms, using the codes provided.

Note: Serious adverse events will be reported on CTEP-AERS using CTCAE v5.0.

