9.0 ADVERSE EVENTS

9.1 Routine Adverse Event Reporting

Adverse event data collection and reporting, which are required as part of every clinical trial are done to ensure the safety of patients enrolled in the studies as well as those who will enroll in future studies using similar agents. Adverse events are reported in a routine manner at scheduled times according to the study calendars in Section 5.0. For this trial, Adverse Events: Baseline, Adverse Events: Solicited and Adverse Events: Other forms are used for routine AE reporting in Rave.

Category (CTCAE SOC)	Adverse Event/ Symptoms	Baseline	Each evaluation	Grading scale (if not CTCAE)
Vascular disorders	Hot flashes	X	X	
	Thromboembolic events			
Metabolism and Nutrition disorders	Hypertriglyceridemia	X	X	
Investigations	Aspartate aminotransferase (AST) increased	X	X	

1. Patients who report visual symptoms in between their baseline and follow-up visits should be evaluated by ophthalmology.

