10.1.7 Adverse events

The most common adverse effects of Z-Endoxifen HCl have been mostly grades 1-2 hot flashes (50%), anemia (25%), fatigue (25%), lymphocyte count decreased (22%), nausea (19%), platelet count decreased (19%), hypertriglyceridemia (16%), irritability (16%), anorexia (13%), AST increased (13%), edema limbs (13%), and WBCs decreased (13%).

Thromboembolic event (grades 3-4) and hypertriglyceridemia (grade 4) have also been reported.

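### Hypertriglyceridemia is to be graded at every evaluation and drives a Z-Endoxifen HCl hold rule, but a triglyceride result is required only at pre-registration and cycles 2, 4 and 8

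*Combined protocol and SAP*

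**What the plan says.** - **Triglyceride schedule.** In both calendars triglycerides appear only in the fasting lipid row, governed by footnote C: "Lipid profile is required at Pre-registration (baseline), cycles 2, 4 and 8 and thereafter at the discretion of the treating physician". The footnote is the same in 5.1 and 5.2. The row is blank in every column for progression or discontinuation.
- **Solicited adverse event.** The Section 9.1 table reads "Hypertriglyceridemia X X", the two marks standing under baseline and each evaluation. Timing follows the calendars: "Adverse events are reported in a routine manner at scheduled times according to the study calendars in Section 5.0". The calendars mark adverse event assessment on day 1 of each cycle and at progression or discontinuation. On cycle length they state: "Cycle length is 21 days".
- **Hold rule.** Section 8.2.2 states: "If a grade 3 or 4 lymphopenia, thrombocytopenia, or hypertriglyceridemia, hold Z-Endoxifen HCl therapy until toxicity resolves to < grade 2". On resolution it adds: "If the toxicities do not resolve to ≤ grade 1 or baseline severity within 21 days (1 cycle), treatment is to be discontinued". The rule is written for Z-Endoxifen HCl, so it covers Arm 1 and the crossover phase.
- **Crossover baseline.** Footnote G of 5.2 states: "Baseline imaging tumor measurements and laboratory studies for patients crossing over to the Z-Endoxifen HCl phase, are those taken at the time of disease progression", meaning progression while taking tamoxifen. Footnote 2 of 5.2, on using labs from before crossover for cycle 1 day 1 if at most 21 days old, is attached to the chemistry and blood count rows but not to the lipid row.
- **Known risk.** Section 10.1.7 gives hypertriglyceridemia in 16% of patients, and adds: "Thromboembolic event (grades 3-4) and hypertriglyceridemia (grade 4) have also been reported".

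**The concern.** Hypertriglyceridemia is graded from a laboratory value. The other items that 8.2.2 names in the same sentence, lymphopenia and thrombocytopenia, are backed by a blood count every cycle and at progression. AST, another solicited item in 9.1, is also drawn every cycle. Only hypertriglyceridemia has a grading schedule denser than its measurement schedule, which looks like an oversight.

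Four parts of the plan use the grade: the hold rule in 8.2.2, the proportion of patients per arm with a grade 2-5 event (13.1.6.1), expedited reporting above grade 2 (9.3), and the grade 4 suspension rule (13.1.7). If no blood is taken, a site completing the solicited form has nothing to grade, and a rise that nobody measured is tabulated as no event. The reported rate can then only be too low. In the crossover phase, 8.2.2 refers to baseline severity and footnote G says where the baseline comes from, but the lipid row has no mark there.

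**Working it through.** The plan states no figure on this point to reproduce, so the check sets the two schedules side by side.

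**Inputs.** Cycle length 21 days (5.1). Required lipid cycles 2, 4 and 8, plus pre-registration (5.1 and 5.2, footnote C). Resolution window 21 days (8.2.2). Median PFS 3.0 months on tamoxifen and 6.0 months on Z-Endoxifen HCl; 40 patients per arm (13.1.3). Assumptions: exponential time to progression, treatment until progression, lipid draws on day 1 of the cycle, 30.44-day months.

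**1. Share of visits with a required result**
- Cycles 2 to 8: 3 of 7 day-1 visits, 43%.
- Cycles 1 to 8: 3 of 8 (38%), or 4 of 8 (50%) if the pre-registration value is credited to cycle 1.
- Cycles 1 to 12: 3 of 12 (25%), or 4 of 12 (33%) with that credit.
- Cycle 9 onward, and at progression or discontinuation: none.

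**2. Gaps between required results**
- Cycle 2 to 4: 2 × 21 = 42 days.
- Cycle 4 to 8: 4 × 21 = 84 days, four times the 21-day resolution window.
- No scheduled result therefore falls within 21 days after a required one, so resolution after a hold would have to be judged on an unscheduled test.

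**3. Patients remaining when the requirement ends**
- Cycle 8 day 1 is 7 × 21 = 147 days after the first dose, and 147 / 30.44 = 4.83 months.
- S = exp(−ln 2 × 4.83 / median).
- Median 6.0 months: S = 0.572, and 0.572 × 40 = 22.9, about 23 Arm 1 patients.
- Median 3.0 months (no benefit over tamoxifen): S = 0.328, and 0.328 × 40 = 13.1, about 13 patients.

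**4. Expected coverage over the whole time on treatment**

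Sum S over all cycle day-1 visits, and over cycles 2, 4 and 8 only.

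| Median | Expected day-1 visits | With a required result | Share | Share with baseline credited |
|---|---|---|---|---|
| 6.0 months | 13.05 | 2.28 | about 17% | 25% |
| 3.0 months | 6.79 | 1.80 | about 26% | 41% |

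**5. Crossover**
- Scans fall at completion of cycles 2, 4 and 6 (5.2, footnote E), that is days 42, 84 and 126.
- The last required lipid draw before each is on day 21 (cycle 2), day 63 (cycle 4) and day 63 (cycle 4).
- Age of that value at the scan: 42 − 21 = 21, 84 − 63 = 21 and 126 − 63 = 63 days.
- Z-Endoxifen HCl may start up to 28 days after documented progression (7.3), so the value could be up to 49, 49 or 91 days old. Footnote 2 accepts the other labs for cycle 1 day 1 only if they are at most 21 days old.
- The lipid row carries C in the crossover column, but footnote C does not say whether cycle numbers restart at crossover.

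**The case against.** The strongest reply is that Section 9.1 defers to the Section 5.0 calendars, and those contain footnote C. On that reading the item is graded when a result is due, and there is no conflict. This is a possible reading, but the table marks each evaluation without qualification, and the protocol does not say what to enter when no result exists.

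Three stronger conclusions are tempting, and the documents do not support them:

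- **That the hold rule cannot operate between required draws.** Section 8.2.2 ties the hold to a grade, not to a visit. Nothing bars an unscheduled test, and footnote C expressly leaves later testing to the physician. The plan fails to guarantee the data; it does not disable the rule.
- **That crossover patients start Z-Endoxifen HCl with no earlier triglyceride value.** Every Arm 2 patient has a required pre-registration profile, and further ones at tamoxifen cycles 2, 4 and 8 if reached. Under the 3.0-month median about 85% would be progression-free at cycle 2 day 1. What is missing is a clear requirement for a new value at the switch.
- **That the blank cell settles the crossover question.** In 5.2 the imaging rows are also blank in the tamoxifen-progression column, although footnotes 3 and G rely on those scans. Footnote G speaks of laboratory studies without excluding lipids. So the requirement is unclear rather than plainly absent.

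Two further points limit the size. The phase I events in 1.6 and 10.1.7 (16%, from 32 patients) are described as mostly grades 1-2, whereas the hold applies to grades 3-4; the current list in 9.3, based on 125 patients, puts the event in the at-most-20% category. Footnote C is also identical in both arms, so sampling per cycle is equal in the randomized phase, and the analysis in 13.1.6.1 is descriptive. Coverage does fall with longer treatment, but the documents give no basis for quantifying the resulting bias.

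**Conclusion.** The point holds as an internal mismatch. The protocol asks for a laboratory grade at each evaluation and builds a hold rule on it, but requires the laboratory value at 3 of the 7 day-1 visits in cycles 2 to 8, with an 84-day gap, and at none afterwards. The visit counts and gaps follow from the calendar alone. The estimate that 33% to 57% of Arm 1 (about 13 to 23 of 40) would still be progression-free when the requirement ends rests on exponential PFS and the two design medians. Quoting only the upper figure would assume that the hypothesized benefit is real.

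The effect on the grade 2-5 proportion is known in direction, toward undercounting, but not in size. At crossover, the baseline that footnote G and 8.2.2 presuppose is not clearly provided for triglycerides, although older values exist. The primary PFS comparison is not affected. This is worth correcting because it concerns a named risk of the investigational drug and the remedy is cheap.

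**What to change.** Reconcile footnote C (5.1 and 5.2), the lipid row of the 5.2 calendar, footnote G, Section 8.2.2 and the Section 9.1 table so that the solicited grading, the hold rule and the crossover baseline all rest on scheduled results. How often triglycerides are measured is for the sponsor to decide. The reconciled text should also say which triglyceride value serves as the crossover baseline and whether footnote C's cycle numbers restart at crossover.

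If the sparser schedule is kept, add a *not assessed* entry to the solicited form for visits without a result. In 13.1.6.1, base the hypertriglyceridemia rate on measured visits and report beside it how many patients had at least one result on treatment. This repairs the reporting only. The sponsor would still need to state what 8.2.2 relies on between results.

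Cost: a calendar and form amendment. If more results are scheduled, blood is already drawn on day 1 of each cycle, so the burden is possible extra fasting and a small assay charge. If they are not, the cost is a smaller and openly stated denominator.
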